2.1.2 Secondary Objectives

- To measure gout flare frequency and health related quality of life.
- To assess treatment adherence measuring oxypurinol, the active metabolite of Allopurinol
- To evaluate the cost-effectiveness and safety of the approach by gathering data including hospital and GP visits and work absenteeism, and adverse events.
- Identification of uric acid load in faecal samples and correlation with gut microbiome characteristics.
- To assess feasibility of implementation, compliance and impact of dietary modification on serum urate levels.

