2.2 ENDPOINTS

2.2.1 Primary Endpoint

- Proportion of participants achieving urate level $\leq 0.30\text{mmol/L}$ at 24 weeks.

2.2.2 Secondary Endpoints (assessed at week 24 and 52, and for extension study also at week 104 and 156)

- Proportion of participants achieving urate level $\leq 0.3\text{mmol/l}$ and $\leq 0.36\text{mmol/l}$
- Prospectively gathered number of days of self-reported gout flare over course of study
- Size in mm of the largest tophus at baseline (index tophus)
- The number of clinically evident tophi
- Prospectively gathered self-reported quality of life during/following gout flare evaluated using the EQ-5D-5L questionnaire over course of study
- Prospectively gathered data on days lost at work due to gout flare over course of study
- Prospectively gathered number of scheduled and unscheduled medical appointments/ hospital admissions due to gout over course of study
- Self report of number of doses of medication omitted in preceding 2 weeks will be collected at all study visits
- Plasma oxypurinol levels will be measured at study visits where possible
- Proportion of patients achieving a dose reduction of urate lowering therapy in the extension phase whilst maintaining target urate levels.
- Proportion of patients achieving sustained dietary modifications with reduction of urate levels, and/or further reduction of urate lowering therapy dose in the extension phase.

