6.1.2 Intervention procedures

Based on the baseline renal function and serum urate levels, and in line with local protocols, an individual treatment plan will be drawn up for all participants in both groups. This includes a management plan for a potential episode of gout-flare and offering of flare prophylaxis. The treatment plan will be sent to the general practitioner and the patient copied in. All participants will be examined at baseline and the number and size of tophi (if present) will be recorded.

All participants will have the GoutSMART application installed on their phones, and be taught how to use the application to allow direct communication between the research staff and the participant. All participants will be given access to online resources providing background information on the causes of gout, the likely progression of symptoms, strategies for dealing with acute attacks of gout and the importance of controlling serum urate levels. All participants will be prompted once per month to enter information about their disease severity including the number of days of flare per month, health related quality of life during and after flares, number of days lost at work and the number of health care appointments attended.

Participants in the intervention group will receive their treatment plan in the same fashion and will be provided with the BeneCheck hand-held device, taught to perform the serum urate finger prick self-test and shown how to enter this information into the application. Participants will be sent automatic reminders two weeks after any increased dose of urate lowering therapy (including that of the plan set during baseline clinic consultation) to test their own urate levels and submit updated readings. If urate levels remain above target, written advice to increase the dose of urate lowering will be sent to the patient and supervising physician advising up-titration of therapy, with this confirmed also by text message. If up-titration is recommended, a reminder to test again will be sent after a further two weeks. Conversely, for participants achieving target levels, acknowledgement will be sent and a request to resubmit readings will be sent on a monthly basis until three consecutive target readings have been obtained. Six months are allowed to ensure that all participants have the opportunity to escalate to maximum therapy and potentially switch to alternative urate lowering therapy if required.

6.1.3 End-of study visit week 24

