
Participants will be invited to the RDU clinic, or alternatively if hospital attendance is not appropriate due to recommendations to self-isolate or maintain social distancing due to the coronavirus pandemic then this assessment will be made by telephone. The patient diaries generated by the GoutSMART application will be reviewed and any adverse advents recorded. Participants will complete a questionnaire on their experience with standard care or the testing device and the smart phone application. All participants will be asked to record the number of doses of medication missed in the preceding 2 weeks. A physical examination will be performed to assess the size and number of tophi, or submitted images will be reviewed. Finger prick and/or serum urate will be measured along with blood tests of full blood count, renal and liver function tests and oxypurinol levels. A letter will be written to the GP of all participants summarising the disease course and management throughout the past 24 weeks and proposing further management advice. All participants will retain access to the smart phone application and be asked to enter information about the disease course on a monthly basis until week 52.

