6.2.3 App assessments

The smart phone application will collect the following data monthly over the 52 weeks of the study

- Number of days of self-reported gout flare
- Self-reported quality of life during/following gout flare evaluated using the EQ-5D-5L questionnaire
- Number of days lost at work due to gout flare
- Number of scheduled and unscheduled medical appointments/ hospital admissions due to gout

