7 DATA COLLECTION

Data will be collected at baseline, week 24 and 52 visits as well as via the smart phone application on a monthly basis. Data will be collected by the principal investigator and the sub-investigators. We will use the EQ-5D® standardized instruments EQ-5D-5L to evaluate health outcome. To maximise completeness of data collection, every effort will be made to contact participants who have failed to attend scheduled visits, submit requested information via the smart phone application or return questionnaires. Participants will be contacted by telephone on at least two occasions.

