9 ADVERSE EVENTS

Adverse side effects from allopurinol and febuxostat are rare, with the commonest side effect being of skin rash. All participants will be informed of potential side effects of their treatment in line with usual clinical practice and be able to contact the study team directly to discuss any concerns. The participants' usual primary care physician will be notified simultaneously with details of any medication change to ensure that the primary care records remain accurate and to minimize the risk of drug interactions.

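### Safety is a stated objective, but adverse events are recorded only at widely spaced visits, the monthly app list does not ask about them, and the sections disagree on which admissions count

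*Combined protocol and SAP*

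**What the plan says.** Section 2.1.2 sets the objective: "To evaluate the cost-effectiveness and safety of the approach by gathering data including hospital and GP visits and work absenteeism, and adverse events". The only instruction to record adverse events is in the week 24 visit (6.1.3), repeated word for word for weeks 52, 104 and 156 (6.1.4): "The patient diaries generated by the GoutSMART application will be reviewed and any adverse advents recorded".

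Section 7 describes the collection points: "Data will be collected at baseline, week 24 and 52 visits as well as via the smart phone application on a monthly basis". Section 6.2.3 opens with "The smart phone application will collect the following data monthly over the 52 weeks of the study" and lists four items: flare days, EQ-5D-5L around flares, work days lost to flare, and "Number of scheduled and unscheduled medical appointments/ hospital admissions due to gout". Section 6.1.2 describes the last two more loosely, as "number of days lost at work and the number of health care appointments attended".

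Section 9 states: "Adverse side effects from allopurinol and febuxostat are rare, with the commonest side effect being of skin rash". It adds that participants will be told about side effects and may contact the study team. It gives no definition of an adverse event, no seriousness grading and no rule for recording what is reported. Adverse events do not appear among the endpoints in 2.2 or in the analyses in 8.2.

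**The concern.** What is new here is dose escalation guided remotely by self-tested urate. Most of the safety information that matters would arise during titration, between visits. As the app list is written, a participant who develops a rash, the side effect the protocol itself calls commonest, has no prompted place to report it. An admission for a drug reaction falls outside an item confined to gout.

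The study is meant to inform a larger trial (8.1, 13.2). A low adverse-event count could then reflect infrequent, unprompted collection as much as a low rate of harm. A difference between arms could reflect unequal contact.

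**Working it through.** The plan gives no safety figure to reproduce. The check compares the schedule and the wording across sections.

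**1. Spacing of recording points.** The visit weeks come from 6.1.3 and 6.1.4, and from the heading of 2.2.2 ("assessed at week 24 and 52, and for extension study also at week 104 and 156"). Gaps: 24 − 0 = 24; 52 − 24 = 28; 104 − 52 = 52; 156 − 104 = 52 weeks. The 52-week gaps occur only in the extension.

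**2. What is asked in between.** Both arms are prompted monthly, so there are about 12 prompts in year 1 against 2 adverse-event recording points. Adverse-event items in the 6.2.3 list: 0 of 4.

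**3. Set against titration.** Intervention participants are reminded to retest two weeks after each dose increase (6.1.2). The arithmetic ceiling before the first recording point is 24 / 2 = 12 cycles.

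**4. Which appointments and admissions count.**

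| Place | Limited to gout? |
|---|---|
| Synopsis, secondary endpoints | Yes |
| 2.2.2 | Yes |
| 6.2.3 | Yes |
| 2.1.2 (objective) | No limit stated |
| 3.1 | No limit stated |
| 6.1.2 | No limit stated |
| 8.2 | No limit stated |

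The version that is built decides whether a drug-reaction admission enters the data.

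**5. Contact by arm.** The two-week reminders go to the intervention arm only. In the extension, usual care has no further titration or outpatient review once at target (3.2), while intervention participants who reduce their dose reassess every two weeks (6.1.4). Unsolicited reports could therefore differ by arm for reasons other than harm.

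**6. What under-capture could do (illustration).** The documents give neither a reaction rate nor a capture fraction, so both are assumed here. With about 60 participants at 2:1, the intervention arm has 60 × 2/3 = 40 and usual care 20. For true risk r and capture fraction c, the chance of recording at least one event among 40 is 1 − (1 − rc)^40:

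| r | c = 1 | c = 0.75 | c = 0.5 |
|---|---|---|---|
| 1% | 33% | 26% | 18% |
| 2% | 55% | 45% | 33% |
| 5% | 87% | 78% | 64% |

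Even with complete capture, zero events leaves a one-sided 95% upper bound of 1 − 0.05^(1/40) = 7.2% in the intervention arm and 1 − 0.05^(1/20) = 13.9% in usual care. Any comparison of arms will be descriptive.

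**The case against.** The strongest reply is that the plan does collect safety information. Adverse events are recorded in both arms at every visit. Visits include a focussed history and examination (6.2.1) and blood tests: full blood count, renal and liver function at week 24, renal and liver function later. Study-specific questionnaires are completed at the four visits (6.2.4). The electronic patient record is a source document (7.1), so an admission for a reaction could be found there whatever the app asks. All participants can communicate with staff directly. With about 60 participants and drugs whose side effects the protocol calls rare, no collection method would give a precise comparison.

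Much of this stands, and it rules out some tempting readings:

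- A reader might infer that the app diary is the sole source of adverse events. The text says diaries are reviewed and events recorded; it does not say the second comes only from the first.
- A reader might infer that treatment-related admissions are certainly lost. The sections conflict, and 8.2 has no gout limit. Equally, 6.1.2 lists appointments under disease severity, so its wording may be shorthand for gout appointments.
- A reader might take 12 cycles as the expected number. It requires an above-target reading every time; participants at target move to monthly readings.

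The reply does not close the gap. The history in 6.2.1 names disease duration and flares, not side effects. Section 3.3 moves scheduled reviews to telephone unless clinically indicated, so examination and bloods may be missing, and a resolved rash would not show in either. No rule requires a search of the record or turns a contact into a recorded event. Someone who leaves before week 24 may never reach a recording point, and 5.3 documents the reason for withdrawal only where possible.

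**Conclusion.** The point holds: the safety objective is not adequately supported by the collection and analysis described. It would be too strong to say that it cannot be answered, because visit recordings, laboratory results where attended and the patient record allow a limited descriptive summary.

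The established defects are gaps of 24 to 28 weeks between recordings in the original study and 52 weeks in the extension, no adverse-event question among the four monthly items, conflicting scope for appointments and admissions, and no adverse-event endpoint or analysis. How many events would be missed cannot be derived from the documents; the table of chances above rests on assumed rates and capture. That contact-driven reporting would differ by arm is a reasonable inference from the unequal prompting, not something the documents state.

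The primary endpoint is unaffected. This is a worthwhile, inexpensive improvement.

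**What to change.** 1. Add one identically worded question on new symptoms or side effects, with onset date, to the monthly app prompt in both arms. Section 6.2.3 describes monthly collection only to week 52, so state whether the question continues in the extension. Without that, the two longest gaps remain.
2. Reconcile the synopsis, 2.2.2, 3.1, 6.1.2, 6.2.3 and 8.2 so that all appointments and admissions are collected, with a reason field: gout, gout treatment, or other. The gout-specific count can still be derived from it.
3. List adverse events and treatment-related admissions in 2.2.2 as a descriptive secondary safety endpoint, and tabulate them by arm in 8.2 from all sources. Show the monthly question separately, with its completion rate by arm, as the like-for-like comparison. It must not displace events found at visits, in laboratory results or in the patient record.

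The cost is an app change, an amendment with its approvals, slightly more participant burden, and staff time to review reports, many of them non-serious. No extra visits or samples are needed. Some original participants will already have passed through titration, but 3.2 plans additional extension participants whose treatment is still to be optimised with the app, so the change would still inform the larger trial.

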6.2.4 Questionnaires

We will use the EQ-5D[®] standardized instruments EQ-5D-5L to evaluate health outcomes. Study specific questionnaires will be completed at week 24, week 52, week 104, and week 156 visits.

Participants will fill an online version of the Scottish Collaborative Group food frequency questionnaire (FFQ) – see Zgaga et al, PLOSone 2012. This comprises a semi-quantitative measure of approximately 150 commonly consumed food items. The questionnaire will also be used for the extension substudy at week 52 and week 3 months and end of study for the extension phase. Participants of the substudy will also fill in a short dietary compliance report.

6.2.5 Biomarker analysis

Participants will be asked to provide an additional sample of about 50ml of venous blood at the baseline visit. In most cases the blood sample will be taken on this single occasion only, but selected participants who have previously consented may be approached and asked to provide an additional blood sample if there is a technical problem with processing the original

sample. The sample will be used for DNA extraction and serum will be separated and stored for biochemical analysis. Analysis of candidate genes thought to be involved in the pathogenesis and response to treatment of gout will be performed using standard methodology. The genes to be studied will include variants identified in the analysis of the Febuxostat versus Allopurinol Streamlined Trial (FAST study) that are found to be associated with response to treatment with urate lowering therapy.

6.2.6 Urinary metabolomics

Fresh urinary samples will be provided in a standard universal container. Samples will be the first void on the morning that the sample is provided.

6.2.7 Faecal samples

Fresh and formed faecal samples will be provided by participants ideally on the day of measurement. Participants will be provided with instructions and equipment to safely and effectively collect and deliver the sample to the research staff.

6.3 STORAGE AND ANALYSIS OF SAMPLES

Routine serum biochemistry samples for U&Es, LFTs, urate and oxypurinol will be analysed and stored by local NHS Lothian laboratories. Samples will be discarded as per local protocols.

For biomarker analysis, DNA extraction will be performed in the research laboratories at the Centre for Genomics and Experimental Medicine, at the Institute of Genetics & Molecular Medicine according to standard procedures. The DNA samples will be stored frozen in these facilities or in another suitable storage facility. It is anticipated that the samples and associated clinical information will be stored indefinitely to allow replication of future genetic studies identifying variants involved in the pathogenesis and response to treatment of gout.

For urinary metabolomic analysis, urinary samples will be centrifuged and aliquoted into 2mls containers. These will be stored at -80 degrees Celsius at the research laboratories of the Centre for Genomics and Experimental Medicine, at the Institute of Genetics & Molecular Medicine.

Formed stool samples will also be delivered by study staff to the research laboratories of the Centre for Genomics and Experimental Medicine, at the Institute of Genetics & Molecular Medicine. Here, DNA extraction will be performed on arrival according to a standardized protocol and samples will be aliquoted before being frozen at -80 degrees Celsius. Urinary samples will subsequently be analysed en masse to quantify levels of metabolites related to purine and uric acid metabolism. Likewise, faecal water will be used to quantify levels of metabolites related to purine and uric acid metabolism. DNA extracted from faecal samples will also be used to characterise the gut microbiome using shotgun metagenomic sequencing.

7 DATA COLLECTION

Data will be collected at baseline, week 24 and 52 visits as well as via the smart phone application on a monthly basis. Data will be collected by the principal investigator and the sub-investigators. We will use the EQ-5D® standardized instruments EQ-5D-5L to evaluate health outcome. To maximise completeness of data collection, every effort will be made to contact participants who have failed to attend scheduled visits, submit requested information via the smart phone application or return questionnaires. Participants will be contacted by telephone on at least two occasions.

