5.2 CONSENTING PARTICIPANTS

Written and informed consent will be obtained by the principal investigator or the sub-investigator prior to any study-related procedures being undertaken. Verbal and written participant information will be presented to the participant detailing the nature of the study, the

implications and constraints of the protocol; the known side effects and any risks involved in taking part. It will be clearly stated that the participant is free to withdraw from the study at any time for any reason and without prejudice to future care, and with no obligation to give the reason for withdrawal. The participant will be allowed as much time as wished to consider the information, and the opportunity to question the Investigator, the GP or other independent parties to decide whether they will participate in the study. Written Informed consent will then be obtained by means of the participant dated signature and dated signature of the person who presented and obtained the informed consent. A copy of the signed Informed Consent will be given to the participants. The original signed form will be retained at the study site.

Patients invited to participate in the extension phase of the study will be provided with written information about the extension via email or in the post with at least 48 hrs time to read the information prior to there week 52 review. Consent will be obtained either during the face to face visit. To minimise COVID-19 exposure, consent may be obtained following a telephone review. The participant may sign the PIL at home and email or post this back to the researcher.

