6.1.4 Follow-up visit week 52 (and for extension study week 104 and 156)

Participants will be invited to the RDU clinic for review of secondary outcomes, or alternatively if hospital attendance is not appropriate due to recommendations to self-isolate or maintain social distancing due to the coronavirus pandemic then this assessment will be made by telephone. The patient diaries generated by the GoutSMART application will be reviewed and any adverse advents recorded. All participants will be asked to record the number of doses of medication missed in the preceding 2 weeks. A physical examination will be performed to assess the size and number of tophi or submitted images will be reviewed. Finger prick and/or serum urate will be measured along with blood tests of renal and liver function tests and oxypurinol levels.

All participants completing the study at week 52 will be offered participation of the extension phase of the study. Written information will have been provided prior to their week 52 review about the extension. Consent will be gained from those choosing to participate in the extension phase. A treatment plan will be formulated for all participants. Participants of the intervention arm in remission will be offered to reduce the dose of their urate lowering medication and self-reassess every two weeks (update urate levels, entering disease activity

data) until remission maintenance is achieved. Feedback will be provided in the usual GoutSMART application manner. Participants of the control arm will continue as per routine care. Once remission maintenance is achieved monthly urate reading will be requested. The participant will be asked to enter additional urate readings and QoL information during flares.

For those opting into the dietary lifestyle intervention arm, a personal management plan with dietary adjustments where appropriate will be formulated based on the Food Frequency Questionnaire which each participant will fill in at baseline. Participants will be asked to perform weekly urate measurements, weight measurements and report on flares via the app. Feedback will be provided by the research team at least weekly for the first 4 weeks, then monthly for three months. Participants will be asked to fill in the Food Frequency Questionnaire at extension baseline, monthly for three months and at the end of study.

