8.2 PROPOSED ANALYSES

The primary outcomes of the study will be the proportion of participants achieving urate level $\leq 0.3\text{mmol/l}$ at 24 weeks in participants receiving supported self-management compared to those receiving usual care. Comparison of proportions will be performed using the Chi-square test of independence, or Fishers Exact test for where expected values in any cell of the contingency table are less than 5, with results displayed as frequency (percentages). The proportion of participants achieving serum urate level $\leq 0.3\text{mmol/l}$ at all subsequent assessments will be analysed in the same fashion. Patients with undetectable levels of oxypurinol will be deemed to be non-compliant and a similar analysis will compare the proportion of participants in each treatment allocation that are non-compliant. For these analyses an intention to treat analysis will be performed with participants that have dropped out of the study being included as failing to reach target, or non-compliant with medication respectively.

Continuous outcome measures include the size in mm of the largest tophus at baseline (index tophus) measured at 52 weeks, and the number of clinically evident tophi evaluated at 52 weeks. Further continuous outcomes include the number of days lost at work due to gout flare, number of scheduled and unscheduled medical appointments/ hospital admissions, self report of number of doses of medication omitted in 2 weeks prior to study visits at week 24 and 52. Two-tailed independent student t-tests will be applied for between group comparisons of normally distributed data. Results will be displayed as mean \pm standard deviation (SD). A Mann Whitney U test (MWU) will be applied when the variables are not normally distributed, with results given as median (interquartile range IQR). Although a nominal value of significance of $p<0.05$ for these exploratory measures will be adopted, given the number of secondary outcomes listed a Bonferroni correction will be applied and reported alongside each result.

Although health reported quality of life data will be gathered this is exploratory data that will not be analysed directly but be used to inform the design of a larger health economic study.

Statistical analysis will be performed using Minitab version 16 (Minitab Inc., Pennsylvania, US) or the Statistical Package for Social Services version 19 (SPSS IBM Corp, NY State, US).

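### Tophus size and number are read without any masking step, so these two exploratory outcomes, and the tophus criterion for remission, are open to detection bias

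*Combined protocol and SAP*

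**What the plan says.** **Who reads.** Section 7 assigns data collection to the investigators: "Data will be collected by the principal investigator and the sub-investigators". The same roles take consent (section 5.2). The visit sections name no separate tophus reader.

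**How tophi are read.** At week 24 (section 6.1.3): "A physical examination will be performed to assess the size and number of tophi, or submitted images will be reviewed". Section 6.1.4 repeats this for week 52 and for the extension visits at weeks 104 and 156: "A physical examination will be performed to assess the size and number of tophi or submitted images will be reviewed". Section 6.2.1 has the presence of tophi recorded and the largest one measured, but gives no instrument, repeat reading or reader standardisation. Section 3.3 makes telephone review the default during the pandemic, so reading from images may be common.

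**What else happens at the visit.** At both week 24 and week 52: "The patient diaries generated by the GoutSMART application will be reviewed and any adverse advents recorded". At week 24 only, section 6.1.3 adds: "Participants will complete a questionnaire on their experience with standard care or the testing device and the smart phone application". Section 6.2.4 lists study-specific questionnaires at weeks 24, 52, 104 and 156 without describing their content at the later visits.

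**How the readings are used.** Section 8.2 compares index tophus size at week 52 and "the number of clinically evident tophi evaluated at 52 weeks" between arms, by t-test or Mann-Whitney U test. It treats these outcomes as exploratory, with a Bonferroni correction reported beside the nominal 5% result. Section 3.2 requires resolution of clinically evident tophi as one of three conditions for remission in the extension.

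**Masking.** The protocol text does not mention blinding, masking, an independent assessor or coded image reading.

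**The concern.** Urate and oxypurinol are laboratory or device values. Deciding whether a swelling is a clinically evident tophus, and where its edges lie in millimetres, is a judgement that can move with the reader's expectation. Participants cannot be masked to this intervention, so masking the reader is the main protection available, and the plan does not use it. The omission is most easily avoided for submitted images, where masking only requires removing labels.

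Two uses of the data are at stake. One is the week 52 between-arm comparison of tophus size and number. The other is the extension: the tophus judgement feeds the remission definition, remission opens the option of dose reduction, and dose reduction is itself a secondary endpoint (section 2.2.2). The study is also meant to inform a larger trial (sections 8.1 and 13.2), so an unmasked reading procedure, or a signal distorted by it, could be carried forward.

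**Working it through.** **Step 1. Is there a plan figure to reproduce?** There is none for tophi: no sample size, power, prevalence or SD. Section 8.1 gives power only for urate (34 against 17, 75% against 25%, stated as 82%). Fisher's exact test on 34 and 17 with 15% drop-out counted as failure (0.75 × 0.85 = 63.75% against 0.25 × 0.85 = 21.25%) gives 81.7%, which agrees. This serves only to confirm the arm sizes used below.

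**Step 2. Can the reader know the arm?** The relevant provisions, side by side:

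| Item | Week 24 (6.1.3) | Week 52 (6.1.4, 6.2.4) |
|---|---|---|
| Tophus examination or image review | yes | yes |
| App diary reviewed at the same visit | yes | yes |
| Questionnaire on standard care or on device and app | yes | not described; an unspecified study questionnaire is listed |
| Reader kept unaware of arm | not stated | not stated |
| Used for tophi in 8.2 | not listed | yes |

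At week 52, the time point that 8.2 uses, nothing prevents the reader from knowing the arm.

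**Step 3. Effect on the estimate.** Let Δ be the true difference in means, and let b_I and b_C be the average reading errors in the intervention and control arms. Then

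E(estimated difference) = Δ + (b_I − b_C).

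No sample size appears in the bias term. A net tilt of 2 mm moves the estimate by 2 mm whether 15 or 51 participants contribute. A Bonferroni correction changes the significance threshold and leaves this term as it is.

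**Step 4. Effect on the test (illustration only).** Tophus prevalence, SD and size of tilt are all assumptions. Set Δ = 0 and let d be the net tilt in SD units; for example, 2 mm with an SD of 5 mm gives d = 0.4. The rejection rate of the two-sided t-test comes from the noncentral t distribution with n1 + n2 − 2 degrees of freedom and noncentrality d / √(1/n1 + 1/n2).

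- 30% of 51 is 15.3, about 10 and 5. For d = 0.4 the noncentrality is 0.4 × 1.826 = 0.73, with 13 degrees of freedom.
- 50% of 51 is 25.5, about 17 and 9. For d = 0.4 the noncentrality is 0.4 × 2.426 = 0.97, with 24 degrees of freedom.

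| With tophi (intervention : control) | d = 0.2 | d = 0.4 | d = 0.6 |
|---|---|---|---|
| 10 : 5, nominal 5% | 6.3% | 10.4% | 17.4% |
| 17 : 9, nominal 5% | 7.5% | 15.4% | 28.7% |
| 10 : 5, Bonferroni over 6 to 10 tests | 0.7% to 1.2% | 1.5% to 2.3% | 3.1% to 4.7% |
| 17 : 9, Bonferroni over 6 to 10 tests | 1.0% to 1.5% | 2.8% to 4.1% | 7.1% to 9.9% |

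Section 8.2 does not give the number of comparisons; 6 to 10 is assumed. In each range the lower figure is for 10 comparisons (threshold 0.05/10 = 0.005) and the higher for 6 (0.05/6 = 0.0083).

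**The case against.** The strongest reply is that this is a feasibility study with a measured primary endpoint, that both tophus outcomes are exploratory, and that every number behind the illustration is assumed. With the Bonferroni result reported alongside, the rejection rate stays below 5% at a 0.4 SD tilt in both scenarios, and at 0.6 SD in the smaller one. This stands as an argument about priority. It does not answer the bias in the estimate, which the correction leaves untouched.

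A reader might also infer four stronger claims, which the documents do not support.

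- *The readers are the people who run the intervention.* This is plausible in one unit but not stated. The application itself suggests dose changes (section 3.1), reminders are automatic, and app contact and feedback are assigned to research staff or the research team (sections 6.1.2 and 6.1.4), without saying who issues titration advice.
- *The visit procedure reveals the arm before tophi are read.* The order of sentences in a visit description is not a mandated order. The arm-specific questionnaire is described only at week 24. Both arms have the app and make the same monthly diary entries, so the diary would reveal the arm mainly through urate or titration content, which is itself an inference.
- *Few participants with tophi make a small tilt decisive.* The figures run the other way: at 0.4 SD the nominal rejection rate is 10.4% with 10 and 5, against 15.4% with 17 and 9.
- *Section 8.2 presents the readings as masked.* It makes no such claim.

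On the remedy, a small team may have no investigator outside a given participant's titration, and participants may disclose their arm. The fix has to allow for both.

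**Conclusion.** The concern holds in a limited form. Judgement-based readings of tophus size and number are made by investigators whom nothing in the plan keeps unaware of allocation. The readings are compared between arms at week 52, and tophus resolution counts toward remission in the extension. The readings could drift toward the intervention arm; whether they would, and by how much, cannot be derived from the documents. Any net drift passes in full into the estimated difference. The effect on the false-positive rate depends on assumed prevalence, SD and tilt: between 6.3% and 28.7% for the nominal test over the range shown, and mostly below 5% after an assumed Bonferroni correction. The primary urate endpoint is not affected. Priority is minor.

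**What to change.** In sections 6.1.3 and 6.1.4:

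1. Have tophi examined before the app diary and questionnaires are opened, by an existing investigator not involved in that participant's titration where one is available.
2. Have submitted images coded, with arm, identity and visit date removed, before the existing reviewer reads them.
3. Add a CRF item recording whether each reading was masked.

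In section 8.2, state that where masking was not possible the tophus comparison is reported as open-label assessment.

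The cost is some scheduling and file relabelling and one CRF field, with no new staff or procedure. Masking will be imperfect because participants may reveal their arm, and the CRF item lets a reader see how often it was achieved.
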